## VERSION HISTORY:

Version No.	Date of issue	Reason for update
1.0	03MAR2017	Initial version for REC/HRA and MHRA submission.
2.0	15MAY2017	Revised version post initial review by the MHRA and REC.
3.0	18JUL2017	Revised version post 2 nd review by the REC.
4.0	19NOV2018	Protocol Amendment 01: Clarification that the requirement for dose delays excludes AEs of ISR, amendment to the exclusion criteria regarding the use of prohibited concomitant steroid medication, amendment to when the expansion cohort can open, requirement for related AEs meeting the stopping rule criteria to be reported as an SAE added, caveat around the use of systemic steroids to treat AEs added, change in container closure system used for the IMP, clarification on imaging requirements and objectives, [REDACTED] change to the lymphocyte count required for inclusion into the study. Other minor changes and clarifications.
5.0	08JUN2021	Protocol Amendment 02: Removal of the control arm in the safety cohort and removal of the expansion cohort; change to end of trial definition; changes to reasons for withdrawal; other minor changes and clarifications.

## LIST OF ABBREVIATIONS AND DEFINITION OF TERMS

	Abbreviation	Definition
A	ABPI	Association of the British Pharmaceutical Industry
	AE	adverse event
	ALK	anaplastic lymphoma kinase
	ALP	alkaline phosphatase
	ALT	alanine aminotransferase
	AML	acute myeloid lymphoma
	ANA	anti-nuclear antibodies
	ANC	absolute neutrophil count
	AST	aspartate aminotransferase
	ATIMP	advanced therapy investigational medicinal product
B	BDU	Biotherapeutics Development Unit
	BP	blood pressure
	BUN	blood urea nitrogen
C	CDD	Centre for Drug Development
	CEA	carcinoembryonic antigen
	CI	Chief Investigator
	CR	complete response
	CRA	Clinical Research Associate
	CRP	c-reactive protein
	CRUK	Cancer Research UK
	CSM	Clinical Study Manager
	CSR	clinical study report
	CT	computerised tomography
	CTA	Clinical Trial Authorisation
	CTCAE	Common Terminology Criteria for Adverse Events
	CXR	chest x-ray
	D	DC
DFS		disease free survival
DMSO		dimethylsulfoxide
E	ECG	electrocardiogram
	eCRF	electronic case report form
	EDC	electronic data capture
	[REDACTED]	[REDACTED]
	ELISPOT	enzyme-linked immunospot
	EoT	End of Trial
	EP	early progression
	ESMO	European Society for Medical Oncology
[REDACTED]	[REDACTED]	[REDACTED]
G	GCP	Good Clinical Practice
	GLP	Good Laboratory Practice
	GMP	Good Manufacturing Practice
	GP	general practitioner
H	Hb	haemoglobin
	HCG	human chorionic gonadotropin
	hESC	human embryonic stem cells
	HIV	human immunodeficiency virus
	HLA	human leucocyte antigen
	HRA	Health Research Authority
hTERT	human telomerase reverse transcriptase	
I	IB	investigator's brochure
	ICD	informed consent document
	ICH GCP	International Conference on Harmonisation of Good Clinical Practice

**LIST OF ABBREVIATIONS AND DEFINITION OF TERMS**

	Abbreviation	Definition
	id	intradermal
	[REDACTED]	[REDACTED]
	IMP	investigational medicinal product
	IND	investigational new drug
	irCR	immune-related complete response
	irPR	immune-related partial response
	irPD	immune-related progressive disease
	irRC	immune-related response criteria
	irSD	immune-related stable disease
	ISR	injection site reaction
	ITF	Investigator Trial File
	IUD	intrauterine device
L	[REDACTED]	[REDACTED]
M	MIA	manufacturing authorisation holder
	[REDACTED]	[REDACTED]
	MHRA	Medicines and Healthcare products Regulatory Agency
	[REDACTED]	[REDACTED]
	MRI	magnetic resonance imaging
	mRNA	messenger ribonucleic acid
N	NCI	National Cancer Institute
	NGS	Next Generation Sequencing
	NHS	National Health Service
	NK	natural killer
	NSCLC	non-small cell lung cancer
	NYHA	New York Heart Association
O	OS	overall survival
P	PBM	peripheral blood monocytes
	PCR	polymerase chain reaction
	PD	progressive disease
	PDF	portable document format
	pH	power of hydrogen (concentration of the hydrogen ion)
	PI	Principal Investigator
	PoP	proof of principle
	PR	partial response
	PS	performance status
	PSRB	Protocol and Safety Review Board
Q	QA	quality assurance
	QC	quality control
	QP	Qualified Person
R	REC	Research Ethics Committee (for the purposes of this trial, the Gene Therapy Advisory Committee will serve as the REC).
	RECIST	Response Evaluation Criteria in Solid Tumours
	RF	rheumatoid factor
	RFS	relapse free survival
	RNA	ribonucleic acid
	[REDACTED]	[REDACTED]
S	SAE	serious adverse event
	SD	stable disease

**LIST OF ABBREVIATIONS AND DEFINITION OF TERMS**

	Abbreviation	Definition
	SDV	source data verification
	SOP	standard operating procedure
	SPD	sum of products of the two largest perpendicular diameters
	SUSAR	suspected unexpected serious adverse (drug) reaction
T	TMF	Trial Master File
	TSH	thyroid stimulating hormone
U	[REDACTED]	[REDACTED]
	UK	United Kingdom
	ULN	upper limit of normal
	USM	urgent safety measure
W	WBC	white blood cell
	WHO	World Health Organisation

## 1 PROTOCOL SYNOPSIS

### 1.1 Full title:

A Cancer Research UK Phase I trial of AST-VAC2 (allogeneic dendritic cell vaccine) administered weekly via intradermal injection in patients with advanced non-small cell lung cancer (NSCLC).

### 1.2 Short title:

A Phase I trial of AST-VAC2 vaccine in patients with non-small cell lung cancer.

### 1.3 Clinical trial objectives and endpoints:

Primary objective	Endpoint
To assess the safety and tolerability of the target dose of AST-VAC2 given as six intradermal (id) injections at Weeks 1, 2, 3, 4, 5 and 6 in patients with advanced NSCLC.	Determining frequency and causality of each adverse event (AE) to AST-VAC2 and grading severity according to the National Cancer Institute (NCI) Common Terminology Criteria for Adverse Events (CTCAE) Version 4.02 or protocol specific grading system for injection site reactions (ISRs).

The secondary and tertiary objectives and endpoints of the trial can be found in [Section 3.1](#).

### 1.4 Trial Design:

This is a first in man, open label, multi-centre Phase I trial to investigate the safety, immunogenicity and patient survival following administration of the dendritic cell (DC) vaccine AST-VAC2 in patients with advanced NSCLC (metastatic or locally advanced).

All enrolled patients will receive AST-VAC2.

Safety review and stopping rule criteria are detailed in [Section 3.3](#). If stopping criteria are met as per protocol, this will trigger an independent review of the data. Pharmacodynamic data will also be reviewed as available.

All potential trial patients will be asked to consent to a pre-screening assessment of Human Leucocyte Antigen (HLA) typing. Once the HLA result is known, patients who are HLA A\*02:01 positive will be asked to consent to participate in the main trial. Patients who are HLA A\*02:01 negative will not be eligible for the trial.

[figure not shown]
Patients receiving AST-VAC2 will be followed up for safety (primary endpoint), pharmacodynamic analyses in blood samples (secondary endpoint) [REDACTED].

All patients will be followed up for up to two years post first vaccination for overall survival and for five years post first vaccination for safety.

### 1.5 Trial treatment:

Patients will receive AST-VAC2 vaccinations, administered by id injection at six time points over a period of six weeks (Figure 1). An interval of 7 days (+/- 1 day) should occur between each of the vaccination days. Two intradermal injections (totalling  $1 \times 10^7$  cells of AST-VAC2) will be administered on each vaccination day. The target administered dose of vaccine is  $1 \times 10^7$  cells of AST-VAC2.

Figure 1. Summary of vaccinations and research sampling

\* Timings may change if vaccinations are stopped before the sixth vaccination

### 1.6 Patient Population:

Up to eight patients with advanced NSCLC will be recruited to the trial. The final number will depend on the number of patient replacements required and vaccine availability.

## 2 INTRODUCTION

### 2.1 Background

#### 2.1.1 Background on non-small cell lung cancer

Primary lung cancer is the most common malignancy after non-melanocytic skin cancer with deaths from lung cancer exceeding those from any other type of malignancy worldwide. While it has been the most important cause of cancer mortality in men since the 1960s, it has equalled breast cancer as a cause of mortality in women since the 1990s. Lung cancer is still increasing both in incidence and mortality worldwide. Non-small-cell lung cancers (NSCLC) account for 85%-90% of lung cancers [1]. In 2014 there were 46,403 new cases of lung cancer in the United Kingdom (UK) [2].

The current treatment strategy for lung cancer should take into account histology, molecular pathology, age, Performance Status (PS), comorbidities, and patient's preference. The European Society for Medical Oncology (ESMO) clinical practice guidelines [3] recommend for the treatment of early stages I and II NSCLC, surgery should be offered to patients who are willing to accept procedure-related risks. The ESMO clinical practice guidelines recommend the first line treatment strategy for locally advanced stage III or metastatic NSCLC patients is a platinum –based doublet chemotherapy, cisplatin-based regimens delivered concurrently with radiotherapy have been studied most extensively and are therefore recommended [1], [3]. Cisplatin based regimens (e.g. cisplatin-etoposide or cisplatin-vinorelbine) have shown higher response rates when compared with carboplatin combinations. The overall survival (OS) was significantly superior for cisplatin in the subgroup of non-squamous cell tumours and in patients treated with third-generation regimens, including gemcitabine and taxanes in one meta-analysis. However, cisplatin-based chemotherapy is associated with more digestive, neuro-, and nephrotoxicity, while hematotoxicity is more often observed with carboplatin [1].

Patients clinically or radiologically progressing after first-line chemotherapy with PS 0-2 should be offered second-line chemotherapy. Comparable options as the second-line therapy consist of pemetrexed or docetaxel. In accordance with ESMO clinical practice guidelines, pemetrexed is preferred to gemcitabine or docetaxel in patients with non-squamous tumours. Pemetrexed use should be restricted to non-squamous NSCLC in any line of treatment [1].

There is increasing interest in identifying sub-populations with potentially treatable molecular abnormalities. Targeted therapies such as tyrosine kinase inhibitors (erlotinib, gefitinib) play a role in patients who have an activating mutation in the relevant pathways such as the epidermal growth factor receptor. Translocations in c-met/anaplastic lymphoma kinase (ALK) or proto-oncogene 1, receptor tyrosine kinase (ROS) can be targeted by crizotinib, another tyrosine kinase inhibitor; however only a minority (<20%) of patients benefit.

Approximately half (47%) of patients diagnosed with lung cancer present with Stage IV disease [2], a fact that is reflected in the survival rates: 32% (1 year), 10% (5 year) and 5% (10 year) [2].

It is estimated that patients with advanced disease, who would be eligible for inclusion in this trial, account for about 47% (Stage IV advanced disease at diagnosis) [2] of the overall lung cancer population.

### 2.2 Investigational medicinal product

For additional information concerning AST-VAC2, refer to the Investigator Brochure (IB).

#### 2.2.1 Structure of AST-VAC2

[REDACTED]

[REDACTED]

[REDACTED]

[REDACTED]

### **2.2.2 Mechanism of action of AST-VAC2**

AST-VAC2 is a DC cancer vaccine which induces an immunogenic response against the tumour associated antigen hTERT.

## **2.3 Safety considerations for the trial**

### **2.3.1 Non-clinical pharmacology**

[REDACTED]

[REDACTED]

[REDACTED]

[REDACTED]

[Redacted]

### 2.3.2 Pharmacokinetics

[Redacted]

### 2.3.3 Toxicology

[Redacted]

[Redacted]

[Redacted]

[Redacted]

[REDACTED]

[REDACTED]

## 2.4 Clinical experience (other compounds in the same class)

This protocol represents a first-in-human clinical trial, accordingly there is no clinical trial experience with AST-VAC2 to date. However there are clinical data generated from Phase I and II oncology trials which administered an investigational agent analogous to AST-VAC2, the autologous DC therapy AST-VAC1.

[REDACTED]

The early phase, proof-of-concept trials supporting AST-VAC1 development were conducted at Duke University Medical Center under investigator-sponsored investigational new drug applications (INDs). These trials enrolled 51 patients and treated 43 patients between December 2001 and May 2006. The majority of trial subjects had metastatic prostate cancer, and lesser numbers had renal cell carcinoma, chronic myeloid leukaemia or chronic lymphocytic leukaemia.

For comprehensive previous clinical data for the above trials, please see the current Investigator Brochure, Section 5.1.2.1.

## 2.5 Rationale for the trial

Novel immunotherapy agents, such as anti-CTLA4 and anti-PD-1 antibodies, as well as vaccines such as TG4010, have demonstrated that NSCLC is amenable to immunotherapy [26-28, 30].

hTERT may be a valuable target in NSCLC. hTERT-specific immune responses were seen in 29 of 44 patients following hTERT peptide (amino acids 611-626 and 540-548) vaccination in patients with Stage III NSCLC, and with immune responders achieving increased survival compared to non-responders. Two subjects are free of disease 8-9 years post-vaccination [13, 14].

While these agents appear to improve outcome, they remain a long way from being able to offer durable term disease control to more than a fraction of patients [29]. The promise that cancer immunotherapy may offer along with the novel properties of AST-VAC2 suggest that the proposed trial is a worthwhile undertaking.

AST-VAC2 has a defined HLA Class I and Class II profile.

[REDACTED]

The HLA A\*02:01 locus is expressed at high frequencies in the general population, including in approximately 46% of individuals of North European Caucasian ancestry [4, 5]. In order to ensure that the patients enrolled in this trial are allogeneically compatible with the hTERT/DC system and thus able to benefit from any therapeutic potential offered, they will be phenotyped prior to inclusion to ensure that they are also HLA A\*02:01 positive. No attempt will be made to match patients to the remaining alleles as it is hoped that this mismatch will induce a beneficial mixed leukocyte reaction.

### 2.5.1 Justification for dose and schedule

The dose of AST-VAC2 proposed for use in the current trial has been selected based on previous clinical experience with autologous DCs [REDACTED] in which a dose of  $1 \times 10^7$  cells was shown to induce anti-hTERT T cell responses in patients with either prostate cancer or acute

## CONFIDENTIAL

myelogenous leukaemia (see [Section 2.4](#) and IB Section 5.1.2.1). In this trial, a target dose of  $1 \times 10^7$  cells has been proposed based on the tolerability of this dose in the AST-VAC1 trial discussed in [Section 2.4](#) and IB Section 5.1.2.1.

Each patient will receive a maximum of six vaccinations based on previous clinical experience with AST-VAC1 in prostate cancer patients, where six vaccinations were found to induce the highest levels of anti-hTERT immune responses. Based on the vaccination regimens used for AST-VAC1, AST-VAC2 will be given at Weeks 1, 2, 3, 4, 5 and 6, 7 days apart (+/- 1 day).

### 3 TRIAL DESIGN

#### 3.1 Clinical trial objectives and endpoints

##### 3.1.1 Primary objectives and endpoints

Primary objective	Endpoint
To assess the safety and tolerability of the target dose of AST-VAC2 given as six id injections at Weeks 1, 2, 3, 4, 5 and 6 in patients with advanced NSCLC.	Determining the frequency and causality of each adverse event to AST-VAC2 and grading severity according to the NCI CTCAE Version 4.02 or protocol specific grading system for ISRs.

##### 3.1.2 Secondary objectives and endpoints

Secondary objectives	Endpoint
To determine the immunogenicity (peripheral response) of AST-VAC2 in patients with advanced NSCLC.	
Observation of the total number of patients showing durable peripheral immune response, defined as a change in one validated assay at two time points after at least two vaccinations.
 
Immunological response will be measured in patient blood by hTERT specific T cells as measured by ELISPOT analysis at the following time points:
 
 
• baseline,
 
• vaccination weeks 3, 4 and 6,
 
• 2 weeks post last vaccination and
 
• 3, 6 and 12 months post first vaccination.
 
 
Immunological change after vaccination is defined as 2.5 fold change over baseline (ratio baseline to post-treatment samples).
 
Individual patient timepoints will be reported as SFU/10^6 PBMCs. Sample will be considered reportable when spot count of peptide pool is greater than peptide pool specific cut-off (as defined in validation).

To document any tumour response(s) in patients receiving the AST-VAC2 vaccine.	Re-assessment of tumour size at end of vaccination visit with Magnetic Resonance Imaging (MRI) or Computerised Tomography (CT) using Immune-Related Response Criteria (irRC).
To determine the 2-year overall survival (OS) in patients receiving the AST-VAC2 vaccine.	Measurement of overall survival at two years post first vaccination.

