4.1 Patient Populations

The analysis sets are defined as follows:

Full Analysis Population (FAP): All patients who enrolled onto the main trial.
Patients who are enrolled in error onto the main trial (due to ineligibility/administrative error), prior to receiving any AST-VAC2 vaccinations, will be excluded from the FAP.

Safety Population: All enrolled patients who received at least one AST-VAC2 vaccination.
This population will also be used for overall survival at 2 years post first AST-VAC2 vaccination. Patients are evaluable for survival regardless of whether they go on to receive another anti-cancer therapy.

HLA Population: All patients who had a sample taken for HLA analysis.
[Redacted]

Secondary Immunogenicity Endpoint Population: All eligible patients who received at least three AST-VAC2 vaccinations and have had a baseline blood sample and at least two post-vaccination blood samples taken.
[Redacted]

Response Population: All eligible patients who have received at least one AST-VAC2 vaccination and have had a baseline assessment of disease and at least one repeat disease assessment measured according to irRC. For details of irRC, refer to Appendix 3 of the study protocol.
If rapid tumour progression occurs before completion of the scheduled six AST-VAC2 vaccinations, the patient will be classified as having early progression. Patients with early progression will be included in the response population.

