5.13.2 Secondary endpoints

5.13.2.1 Identification of peptide specific T cells (Secondary Immunogenicity Endpoint Population)

Immunological response will be measured in whole blood (PBMCs) by hTERT specific T cells as measured by ELISPOT analysis at the following time points:

- baseline,
- vaccination weeks 3, 4 and 6,
- 2 weeks post last vaccination and
- 3, 6 and 12 months post first vaccination.

Vaccine induced ELISPOT response in blood will be reported longitudinally for each patient. The total number of patients showing durable peripheral immune response, defined as a change in one validated assay at two time points after at least two vaccinations (where a change is defined as 2.5 fold change over baseline [after removal of background], assay control and >35 spots/ 10^6 cells) will be reported.

Interim reports are expected at timepoints to be agreed between the Sponsor and the laboratory. Interim reports will be provided within one month of completing the agreed patient analyses. A final report is expected no more than 10 weeks after the last sample is analysed.

The data will be reported in tables and graphs/figures. No formal statistical analysis is planned. The results will be summarised in the CSR and the final report included as an appendix.

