To determine the immunogenicity (peripheral response) of AST-VAC2	Observation of the total number of patients showing durable peripheral immune response, defined as a change in one validated assay at two time points after at least two vaccinations.	
Measure Title: Number of Participants Showing a Durable Peripheral Immune Response
 
Measure Description: Immunological response in whole blood (peripheral blood mononuclear cells) by human telomerase reverse transcriptase (hTERT) specific T cells measured by enzyme-linked immunospot (ELISPOT), with a durable peripheral immune response defined as a change in one validated assay at two time points after at least two vaccinations (where a change is defined as 2.5 fold change over baseline [after removal of background], assay control and >35 spots/10⁶ cells).
 
Time Frame: Screening, vaccination weeks 3, 4 and 6; 2 weeks post last vaccination and 3, 6 and 12 months post first vaccination.
 
Measure Type: Count of participants
 
Measure of dispersion/precision: Not applicable
 
Measure Title: Mean Fold Change in hTERT Specific T Cells Over Baseline by Timepoint
 
Measure Description: Immunological response in whole blood (peripheral blood mononuclear cells) by hTERT specific T cells measured by ELISPOT and presented as mean fold change in spots/10⁶ cells (after removal of background) from baseline to each timepoint assessed.
 
Time Frame: Screening, vaccination weeks 3, 4 and 6; 2 weeks post last vaccination and 3, 6 and 12 months post first vaccination.
 
Measure Type: Mean
 
Measure of dispersion/precision: Full range

To document any tumour response(s) in patients receiving the AST-VAC2 vaccine.	Re-assessment of tumour size at end of vaccination visit with MRI or CT using Immune-Related Response Criteria (irRC).	
Measure Title: Tumour Response According to Immune-Related Response Criteria (irRC) Post Vaccination
 
Measure Description: Number of participants with complete response, partial response, stable disease, progressive disease or who

		
were not evaluable at radiological disease assessment (computerised tomography and/or magnetic resonance imaging) at the End of Vaccination visit according to irRC (Appendix 3 of protocol).
 
Time Frame: Baseline to End of Vaccination visit (30 days post last vaccination).
 
Measure Type: Count of participants
 
Measure of dispersion/precision: Not applicable

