To determine the 2-year overall survival (OS) in patients receiving the AST-VAC2 vaccine.	Measurement of overall survival at two years post first vaccination.	
Measure Title: Overall survival at 2 Years Post First Vaccination
 
Measure Description Number of participants alive at 2 years post their first vaccination.
 
Time Frame: From first AST-VAC2 vaccination to 2 years post first vaccination.
 
Measure Type: Count of participants
 
Measure of dispersion/precision: Not applicable

7.5.1 Outcome Measure 1 – Frequency and causality of AEs and SAEs to AST-VAC2 (*Safety Population*)

The following table will be programmed to provide results for frequency and causality of AEs and SAEs to AST-VAC2.

Arm/Group Title		Experimental: AST-VAC2
Frequency and causality of AEs, SAEs and Grade ≥3 AEs to AST-VAC2		<N>
Measure type: Number	Number of participants analysed	
Unit of measure: not applicable		
	SAEs	<data>
	Non-serious AEs	<data>
	Grade ≥3 AEs	<data>
	Related SAEs	<data>
	Related non-serious SAEs	<data>
	Related Grade ≥3 AEs	<data>

7.5.2 Outcome Measure 2 - Number of participants experiencing ISRs by grade (*Safety Population*)

The following table will be programmed to provide results for number of participants experiencing ISRs Grade 1 to 4.

Arm/Group Title		Experimental: AST-VAC2
Participants experiencing ISRs Grade 1 to 4		<N>
Measure type: Count of participants	Number of participants analysed	
Unit of measure: participants		
	Grade 1	<data>
	Grade 2	<data>
	Grade 3	<data>
	Grade 4	<data>

7.5.3 Outcome Measure 3 – Number of participants showing a durable peripheral immune response (*Secondary Immunogenicity Endpoint Population*)

The following table will be programmed to provide results for the number of participants with a durable peripheral immune response.

Arm/Group Title		Experimental: AST-VAC2
Participants showing a durable peripheral immune response		<N>
Measure type: Count of participants Unit of measure: participants	Number of participants analysed	
	Durable response	<data>
	Non-durable response	<data>
	Undetermined (baseline sample did not pass acceptance criteria or insufficient timepoints)	<data>

7.5.4 Outcome Measure 4 – Mean fold change over baseline by timepoint (*Secondary Immunogenicity Endpoint Population*)

The following table will be programmed to provide results for the mean fold change from baseline.

Arm/Group Title		Experimental: AST-VAC2
Overall Number of Participants Analysed		<N>

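### ELISPOT samples are reportable only above a spot-count cut-off, so valid low results can drop out; the rule conflicts with the SAP's definition of a change and should be replaced by an assay-validity rule

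*Protocol*

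**What the plan says.** Protocol 3.1.2 (secondary immunogenicity endpoint) and SAP section 2 carry the same sentence: "Sample will be considered reportable when spot count of peptide pool is greater than peptide pool specific cut-off (as defined in validation". It applies to any sample, baseline included. Neither document gives the cut-off or says what happens to a sample that is not reportable.

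The definition of a change differs between the two documents:

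- Protocol 3.1.2: "Immunological change after vaccination is defined as 2.5 fold change over baseline (ratio baseline to post-treatment samples".
- SAP 5.13.2.1, repeated in 7.5: "where a change is defined as 2.5 fold change over baseline [after removal of background], assay control and >35 spots" per million cells.

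A durable response is "defined as a change in one validated assay at two time points after at least two vaccinations". The SAP 4.1 immunogenicity population consists of eligible patients with at least three vaccinations who "have had a baseline blood sample and at least two post-vaccination blood samples taken".

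Two registry tables use these results. Outcome Measure 3 (SAP 7.5.3) has a durable row, a row "Non-durable response", and a row "Undetermined (baseline sample did not pass acceptance criteria or insufficient timepoints". Outcome Measure 4 (SAP 7.5.4) is headed in SAP 7.5 by "Measure Title: Mean Fold Change in hTERT Specific T Cells Over Baseline by Timepoint" and has a separate number analysed at each visit. The SAP does not say how a sample enters that number, or what makes time points insufficient.

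**The concern.** Whether a sample is reportable should turn on assay quality: cell viability, controls, background. Here it turns on the spot count, which is the outcome. A technically sound sample with a low count is a real observation that the vaccine did not raise the response at that visit. If it yields no reported value, missingness is decided by the result.

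Three consequences follow if the sentence is applied as written:

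- The mean fold change is taken over high counts only and is biased upward.
- A patient with fewer than two above-cut-off samples can be recorded as undetermined rather than as lacking a durable response.
- A baseline at or below the cut-off leaves the fold change with no reportable denominator.

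Protocol section 13 names durable immune response as a factor in further development, and both measures are to be posted publicly. With at most eight patients, each lost sample matters.

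**Working it through.** There is no planned figure to reproduce: the analysis is descriptive, with no power or error rate. The check compares the rules and then illustrates the size.

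**1. The rules side by side.** Take a post-vaccination sample that passes assay control but has a low count. Under SAP 5.13.2.1 it fails the spot condition, so it is a valid 'no change'. Under Protocol 3.1.2 and SAP section 2 it is not reportable. One sample, two outcomes, and no text to choose between them.

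**2. Fixed example.** Assumed: eight patients, each with baseline 20; post-vaccination counts 5, 10, 15, 20, 25, 30, 60, 120; cut-off 35.

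- All samples: 285 / (8 × 20) = 1.78.
- Only the two post-vaccination counts above 35: (3.0 + 6.0) / 2 = 4.50, n = 2.

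This applies the rule to post-vaccination samples only. Applied to baseline as well, a baseline of 20 is itself not reportable and none of the eight fold changes exists, including the 3-fold and 6-fold rises.

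**3. No vaccine effect, rule applied to baseline and post-vaccination samples.** Assumed: cut-off 35; independent lognormal baseline and post-vaccination counts with common median m and log-SD s. Let a = ln(35/m)/s and Q(x) be the upper normal tail.

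- Mean fold, all post-vaccination values (baseline > 35): exp(s²) × Q(a+s) / Q(a).
- Mean fold, reportable post-vaccination values only: the above × Q(a−s) / Q(a).
- Share of post-vaccination samples dropped: 1 − Q(a).

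| m | s | Dropped | Mean, all | Mean, reportable only |
|---|---|---|---|---|
| 40 | 0.5 | 39% | 0.87 | 1.11 |
| 40 | 0.8 | 43% | 0.88 | 1.30 |
| 60 | 0.5 | 14% | 1.07 | 1.18 |
| 60 | 0.8 | 25% | 1.14 | 1.41 |

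For m = 40, s = 0.8: a = −0.167, so 1.896 × 0.263 / 0.566 = 0.88, and 0.88 × 0.833 / 0.566 = 1.30. A simulation of 2,000,000 pairs gives the same figures. Only the gap between the last two columns is due to the rule.

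**4. Chance of falling under 'Undetermined'.** There are seven post-baseline time points (weeks 3, 4 and 6; two weeks after the last vaccination; 3, 6 and 12 months). Suppose only reportable samples count, fewer than two is insufficient, time points are independent, and baseline is fixed with no vaccine effect. With p = Q(ln(35/baseline)/s), the chance is (1−p)^7 + 7p(1−p)^6.

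| Baseline | s | p | P(fewer than 2 of 7) |
|---|---|---|---|
| 20 | 0.5 | 0.132 | 0.77 |
| 30 | 0.5 | 0.379 | 0.19 |
| 40 | 0.3 | 0.672 | 0.006 |

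The first two rows again require the baseline to be exempt from the rule.

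**5. Number of durable responders.** A durable response needs a change at two time points. A sample that is not a change adds nothing to that count, kept or dropped. The baseline route is different: without a reportable denominator a rise cannot be credited, so the count could fall. A pool cut-off above the equivalent of 35 spots per million could also exclude a qualifying sample; the documents do not relate the two thresholds.

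**The case against.** The strongest reply is that the plan can be read so that negatives stay in. The population is defined by samples taken, not samples reportable. SAP 7.5 takes the fold change to each time point assessed. A row for patients without a durable response exists. Results are reported longitudinally for each patient. Protocol 3.4.3 treats the absence of an immune response at three months as something that can be observed. A separate number analysed per visit is needed anyway for deaths, missed samples and assay failures, so it does not show that negatives are removed.

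All of that stands, and it limits the point. A reader might infer that the plan averages positives only and reclassifies all-negative patients as undetermined. The documents do not say so: nothing states that non-reportable samples are missing, and the cut-off is neither called a positivity threshold nor equated with 35. A reader might also infer an inflated responder rate, such as 2 of 4 instead of 2 of 8. The plan computes no rate among determined patients; the measure is a count, and 'Undetermined' is a row within those analysed.

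The stakes are modest too. Mean fold change is not a protocol endpoint; it appears only among the ClinicalTrials.gov measures, whose programmed tables stay outside the clinical study report. It is shown with its n and full range, and the laboratory report is appended to the study report.

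What the reply does not do is settle the conflict. None of these passages overrides the reportability sentence or says how a low value is entered.

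**Conclusion.** The point holds as a conflict between two stated rules, one of which makes reporting depend on the outcome. Applied as written, that rule can bias the mean fold change upward, blur the line between undetermined and non-durable, and leave low baselines without a usable fold change. It is more than missing detail, because following the stated sentence gives a worse analysis than following SAP 5.13.2.1.

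For the four no-effect settings in the first table, the mean rises by between 0.11 (1.07 to 1.18) and 0.42 (0.88 to 1.30). At a median of 40 an apparent fall becomes an apparent rise. Lower assumed baselines give larger gaps, but only if the baseline is exempted from the rule. Every size rests on an assumed cut-off of 35, assumed medians and log-SDs, and independence; none of these is in the documents. The number of durable responders is not changed by dropping post-vaccination negatives. The change should be made, but it concerns a descriptive secondary analysis in up to eight patients.

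**What to change.** In Protocol 3.1.2 and SAP 2, 5.13.2.1, 7.5.3 and 7.5.4:

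- Define a sample as reportable when it passes assay control.
- Count a valid post-vaccination result at or below the cut-off as 'no change' for durable response.
- Keep every valid sample, baseline included, in the fold-change summary at its measured background-subtracted value.
- Pre-specify one floor, applied equally to baseline and post-vaccination values, solely to avoid zero denominators.
- Limit 'Undetermined' to missing samples or assay-control failure.

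Low values should not be set to the cut-off. In the fixed example, doing so for post-vaccination values alone gives (6 × 1.75 + 3 + 6) / 8 = 2.44 against the measured 1.78, which is again biased upward. Raising both sides to 35 gives (6 × 1 + 60/35 + 120/35) / 8 = 1.39, which shrinks real rises. Hence a floor used only against zeros.

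The cost is wording in the protocol, the SAP and the laboratory report, with no new samples. The mean fold change may look less favourable.
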